2.6.3.1 Handling of missing values/censoring/discontinuations

Patients in the dose escalation part who are ineligible for the DDS will be excluded from the primary statistical analysis, although their data will be used for all remaining analyses.

Patients in the phase II part who have BOR of Unknown (UNK) or not assessed (NA) will be considered as a treatment failure in the primary analysis of ORR. Patients with individual scans of UNK or NA will be handled according to RECIST 1.1 as per [CLAG525X2101C Amendment 10 Appendix 1].

Other missing data will simply be noted as missing on appropriate tables/listings.

2.7 Analysis of the secondary variables

2.7.1 Efficacy definitions

Best overall response (BOR)

The BOR is the best response recorded from the start of the treatment until disease progression/recurrence. For RECIST v1.1 and irRC, any assessments taken before the start of any further antineoplastic therapy will be considered in the assessment of BOR in recognition that response to immunotherapy may be delayed. For both RECIST v1.1 and irRC, if any alternative antineoplastic therapy is taken while on study, any subsequent assessments will be excluded from the BOR determination.

Per RECIST v1.1, CR and PR need to be confirmed with at least two determinations of CR or PR respectively at least 4 weeks apart before progression. In order to classify overall response as SD, a patient must have at least one SD assessment (or better) > 6 weeks after start date of study treatment. In order to classify overall response as PD, a patient must have progression < 12 weeks after start date of study treatment.

Per irRC, irCR, irPR and irPD need to be confirmed with at least two determinations of irCR or irPR or irPD, respectively at least 4 weeks apart. In order to classify overall response as irSD, the patient must have at least one SD assessment (or better) > 6 weeks after start date of study treatment.

Overall response rate (ORR) and Disease control rate (DCR)

ORR is the proportion of patients with a best overall response of CR or PR (RECIST v1.1) or of irCR or irPR (irRC). DCR is the proportion of patients with a best overall response of CR, PR, or SD (RECIST v1.1) or of irCR, irPR, or irSD (irRC). For phase I single agent and combination tables, NCRNPD (RECIST v1.1) or iNCRNPD (irRC) are included in the calculation of DCR.

Progression free survival (PFS)

For assessment per RECIST v1.1, PFS is the time from date of start of treatment to the date of event defined as the first documented progression or death due to any cause. If a patient has not

had an event, PFS is censored at the date of last adequate tumor assessment [[CLAG525X2101C Amendment 10 Appendix 14.3](#)].

Duration of response (DOR)

DOR applies only to patients with a BOR of confirmed CR or PR (RECIST v1.1). For assessment per RECIST v1.1, DOR is defined as the time from the date of the first documented response (CR or PR) to the date of first documented progression, or death due to study indication.

Time to response (TTR)

TTR applies only to patients with a BOR of confirmed CR or PR (RECIST v1.1). For assessment per RECIST v1.1, TTR is the time between date of start of treatment until first documented response (CR or PR).

Use of alternative cancer therapy

For both RECIST v1.1 and irRC, if any alternative cancer therapy is taken other than palliative radiotherapy or biopsy any subsequent assessments will be excluded from the analysis of endpoints based on tumor response assessments.

Date of last contact

If the patient is not known to have died, the date of last contact will be used. All data excluding the biomarker date will be used to find the date of last contact.

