## 7.2 Assessment types

### 7.2.1 Efficacy assessments

Tumor response will be determined locally according to two sets of criteria:

1. RECIST v1.1 ([Appendix 1](#))
2. irRC ([Appendix 2](#))

The local investigator's assessment will be used for the analysis of response according to both RECIST 1.1 and irRC, and for treatment decision making (study discontinuation due to PD as per irRC). Patients experiencing progressive disease per RECIST v. 1.1 criteria may continue to be treated according to irRC guidelines until progression is documented via irRC. Imaging data may be centrally collected and checked for quality by an imaging Contract Research Organization (CRO) designated by Novartis. The local investigator's assessment will be used for the data analysis and for treatment decision making. Central review of the imaging data may be performed if deemed necessary.

At screening, all patients will undergo CT with i.v. contrast of the chest, abdomen and pelvis. MRI should only be used to evaluate sites of disease that are not adequately imaged by CT. If a patient is intolerant of iodine-based contrast agents, CTs may be performed without contrast. MRI may be used to evaluate sites of disease where a CT without i.v. contrast is not adequate. Visible skin lesions and easily palpable subcutaneous tumors may be measured by physical examination using a ruler or calipers. Ultrasound should not be used to measure sites of disease. See [Table 7-2](#) for further details.

Tumor assessments will be performed at the following time points:

- Screening
- Every 8 weeks  $\pm$  1 week after Cycle 1 Day 1 until 40 weeks, then every 12 weeks  $\pm$  1 week until progression of disease per irRC or patient withdrawal. After EOT, during disease progression f/u, every 8 weeks  $\pm$  1 week until 40 weeks, then every 12 weeks  $\pm$  1 week until progression of disease per irRC, or lost to follow-up.
- PR or CR, per both RECIST 1.1 and irRC, will be confirmed by a new assessment after at least 4 weeks. Also PD, as per irRC, needs to be confirmed after at least 4 weeks.
- At the End of Treatment, if a scan was not conducted within 30 days prior to End of Treatment

Disease progression follow-up should be performed as described in [Section 7.1.5](#).

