#### **14.1.17 Best overall response**

The best overall response is the best response recorded from the start of the treatment until disease progression/recurrence (taking as reference for PD the smallest measurements recorded since the treatment started). In general, the patient's best response assignment will depend on the achievement of both measurement and confirmation criteria.

The best overall response will usually be determined from response assessments undertaken while on treatment. However, if any assessments occur after treatment withdrawal the protocol should specifically describe if these will be included in the determination of best overall response and/or whether these additional assessments will be required for sensitivity or supportive analyses. As a default, any assessments taken more than 150 days after the last dose of study treatment will not be included in the best overall response derivation. If any alternative cancer therapy is taken while on study any subsequent assessments would ordinarily be excluded from the best overall response determination. If response assessments taken after withdrawal from study treatment and/or alternative therapy are to be included in the main endpoint determination, then this should be described and justified in the protocol.

Where a study requires confirmation of response (PR or CR), changes in tumor measurements must be confirmed by repeat assessments that should be performed not less than 4 weeks after the criteria for response are first met.

Longer intervals may also be appropriate. However, this must be clearly stated in the protocol. The main goal of confirmation of objective response is to avoid overestimating the response rate observed. In cases where confirmation of response is not feasible, it should be made clear when reporting the outcome of such studies that the responses are not confirmed.

- -For non-randomized trials where response is the primary endpoint, confirmation is needed.
- -For trials intended to support accelerated approval, confirmation is needed
- For all other trials, confirmation of response may be considered optional.

The best overall response for each patient is determined from the sequence of overall (lesion) responses according to the following rules:

- CR = at least two determinations of CR at least 4 weeks apart before progression where confirmation required or one determination of CR prior to progression where confirmation not required

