- PR = at least two determinations of PR or better at least 4 weeks apart before progression (and not qualifying for a CR) where confirmation required or one determination of PR prior to progression where confirmation not required
- SD = at least one SD assessment (or better) > 6 weeks after randomization/start of treatment (and not qualifying for CR or PR).
- PD = progression ≤ 12 weeks after randomization/ start of treatment (and not qualifying for CR, PR or SD).
- UNK = all other cases (i.e. not qualifying for confirmed CR or PR and without SD after more than 6 weeks or early progression within the first 12 weeks)

Overall lesion responses of CR must stay the same until progression sets in, with the exception of a UNK status. A patient who had a CR cannot subsequently have a lower status other than a PD, e.g. PR or SD, as this would imply a progression based on one or more lesions reappearing, in which case the status would become a PD.

Once an overall lesion response of PR is observed (which may have to be a confirmed PR depending on the study) this assignment must stay the same or improve over time until progression sets in, with the exception of an UNK status. However, in studies where confirmation of response is required, if a patient has a single PR (≥30% reduction of tumor burden compared to baseline) at one assessment, followed by a <30% reduction from baseline at the next assessment (but not ≥20% increase from previous smallest sum), the objective status at that assessment should be SD. Once a confirmed PR was seen, the overall lesion response should be considered PR (or UNK) until progression is documented or the lesions totally disappear in which case a CR assignment is applicable. In studies where confirmation of response is not required after a single PR the overall lesion response should still be considered PR (or UNK) until progression is documented or the lesion totally disappears in which case a CR assignment is applicable.

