4.3.3 Best overall response

Assessment of BOR will be based on all assessments up to and including the first assessment of irPD (cPD1, cPD2, or uPD). Assessments made after start of new anti-cancer therapy, will be excluded.

BOR will be defined with the following hierarchy:

- irCR Two consecutive determinations of irCR ≥ 28 days (4 weeks) apart
Non-consecutive assessments of irCR may also result in BOR of irCR if all intervening assessments are irUNK
- irPR Two determinations of irPR (or better) ≥ 28 days (4 weeks) apart
The two determinations of irPR (or better) may be separated by one or more assessments of irSD, but may not be separated by an assessment of irPD
- irSD At least one irSD assessment (or better) > 42 days (6 weeks) after first treatment
- irPD Event flagged as cPD1, cPD2 or uPD ≤ 84 days (12 weeks) after first treatment
- irUNK All other cases

4.3.4 Time to event analyses:

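### SAP 2.7.1 states RECIST confirmation of PR without the protocol's *or better*, so read literally a PR followed by a single CR is not counted as a response

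*SAP*

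**What the plan says.** Confirmation applies in this trial. Protocol 7.2.1 states that "PR or CR, per both RECIST 1.1 and irRC, will be confirmed by a new assessment after at least 4 weeks".

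Protocol 14.1.17 (Appendix 1) gives the two RECIST rules separately:

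- for complete response, "CR = at least two determinations of CR at least 4 weeks apart before progression where confirmation required";
- for partial response, "PR = at least two determinations of PR or better at least 4 weeks apart before progression (and not qualifying for a CR").

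SAP 2.7.1 merges them into one sentence: "CR and PR need to be confirmed with at least two determinations of CR or PR respectively at least 4 weeks apart before progression". It then sets the fallback category: for SD, "a patient must have at least one SD assessment (or better) > 6 weeks after start date of study treatment". The following paragraph uses the same merged form for irCR, irPR and irPD. SAP 4.3.3 later spells out the irRC rule as "Two determinations of irPR (or better) ≥ 28 days (4 weeks) apart".

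SAP 2.6.2 defines the primary ORR as the share of patients whose best overall response is CR or PR by investigator assessment under RECIST 1.1. SAP 2.7.1 limits DOR and TTR to patients with a confirmed CR or PR.

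**The concern.** The protocol lets a CR confirm an earlier PR. The SAP sentence asks for two of the same kind. The two rules diverge for a patient who shows one PR, deepens to CR, and then has no second CR because of progression, new therapy, an unevaluable scan or the end of assessments.

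A later PR cannot repair this. Protocol 14.1.17 says that after a CR the status cannot fall to anything other than PD, apart from unknown. Once the patient has moved from a single PR to CR, only a second CR would satisfy the SAP sentence.

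At stake is the responder count in the primary ORR, and with it membership of the DOR and TTR populations. DCR would not change, because SD counts towards it. The same patient could also be irPR under SAP 4.3.3 and SD under RECIST purely because of how the sentence was drafted.

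**Working it through.** **1. Apply both rules to response sequences.** Assume that the PR and the first CR are at least 4 weeks apart and that the last response falls more than 6 weeks after the start of treatment. The first scan is due at week 8 ± 1 (protocol 7.2.1), so the 6-week condition for SD is normally met.

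| Sequence | Protocol 14.1.17 | SAP 2.7.1, literal |
|---|---|---|
| PR-PR | PR | PR |
| PR-PR-CR-PD | PR | PR |
| PR-CR-CR | CR | CR |
| PR-CR-PD | PR | SD |
| SD-PR-CR-UNK | PR | SD |
| PR-UNK-CR-PD | PR | SD |

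Only sequences with exactly one PR and one CR differ.

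**2. Size per patient.** 1/40 = 2.5 points; 1/20 = 5 points.

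**3. Reproduce the plan's posterior figures.** The prior is Beta(0.25, 1) (SAP 2.6.2). With r responders out of 40, the posterior is Beta(0.25 + r, 1 + 40 − r).

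- NSCLC, renal, mesothelioma, r = 12: Beta(12.25, 29), P(ORR > 20%) = 0.9228; the plan states 92.3%.
- TNBC, r = 8: Beta(8.25, 33), P(ORR > 10%) = 0.9658; the plan states 96.6%.
- Melanoma, r = 18: Beta(18.25, 23), P(ORR > 30%) = 0.9715; the plan states 97.2%.

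All three agree.

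**4. One affected patient exactly at the threshold.**

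| Group | Protocol rule | SAP literal |
|---|---|---|
| NSCLC, renal, mesothelioma | 12/40, 92.3%, bar met | 11/40, 85.6%, bar missed |
| TNBC | 8/40, 96.6%, bar met | 7/40, 91.7%, bar missed |
| Melanoma | 18/40, 97.2%, bar met | 17/40, 94.3%, bar missed |

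This is the worst placement of a single patient. Any one misclassification at the threshold would do the same, so the table shows sensitivity and not an expected effect.

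**5. Illustration over an assumed frequency.** Let f be the share of confirmed responders with the affected pattern. The documents give no value, so f is purely an assumption. The effective response rate is then ORR × (1 − f). The design is two-stage: expand if at least 3 of the first 20 respond, then require at least 12 of 40. With f = 0 and a true ORR of 40%, the exact two-stage binomial gives 92.8%, matching protocol Table 10-3.

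| Assumed f | Effective ORR | P(≥ 12/40) |
|---|---|---|
| 0 | 40.0% | 92.8% |
| 2% | 39.2% | 91.3% |
| 5% | 38.0% | 88.6% |
| 10% | 36.0% | 82.9% |

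The calculation also thins the first-stage count. The protocol's expansion rule accepts irRC responses as well, so this slightly overstates the loss. The overstatement is negligible: with no first-stage rule at all, the last row would be 83.0%.

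**6. Look for text in the SAP that would override the sentence.** Sections 2.6.2 and 2.6.3 refer to RECIST 1.1 in general terms. Section 2.6.3.1 points to protocol Appendix 1 only for individual scans that are unknown or not assessed. Section 2.7.2 points to Appendix 14.3 for tumour response, but that appendix holds the Bayesian models; the response rules are in Appendix 14.1. No SAP text gives 14.1.17 precedence over 2.7.1.

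**The case against.** The best defence is that 2.7.1 is a prose summary and the SAP itself shows what its shorthand means. The irRC sentence in the same section has the same form, and 4.3.3 expands it to "Two determinations of irPR (or better) ≥ 28 days (4 weeks) apart". The SAP is based on Protocol Amendment 10, whose Appendix 1 carries the full algorithm. Protocol 14.1.29 requires deviations to be defined in the analysis plan at the latest, and none is declared. Derived-variable specifications sit in a separate programming document that is not available here. Nor is there a substantive reason for a CR not to confirm a PR: non-nodal targets have gone and target nodes have shrunk from at least 15 mm to below 10 mm, a fall of more than (15 − 10)/15 = 33%, which exceeds the 30% needed for PR.

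Much of this stands. A reader might infer that the SAP deliberately applies a stricter rule to RECIST than to irRC. The documents do not support that: 2.7.1 words both criteria alike, and loose drafting is the likelier explanation. Nor do they establish that the derivation was programmed literally.

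What does not stand is that this makes the sentence harmless. The irRC rule is spelled out later in the SAP, whereas the RECIST rule, which drives the primary endpoint, is not. A programmer following 2.7.1 as written would reach a classification that the protocol does not give.

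**Conclusion.** The inconsistency is real and narrow. SAP 2.7.1 and protocol 14.1.17 classify a patient with one PR and one later CR differently, and the protocol's classification should stand because no change was declared. The consequence depends on a literal reading of the SAP sentence. If it is read that way, each affected patient lowers the primary ORR by 2.5 points at n=40 or 5 points at n=20, and leaves the DOR and TTR populations. The direction is always downward, so it could not create a false activity signal.

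Two stronger conclusions are tempting and unsupported. One is that ORR is understated for deepening responses in general: PR-PR-CR and PR-CR-CR are unaffected. The other is that the reported ORR will be too low: the documents give neither a frequency for the pattern nor the programmed derivation, and the 2% to 10% range above is illustrative only. Patients still awaiting a confirmatory scan at cut-off should also be few, since SAP 2.1 bases the final report on data up to the point when all patients have potentially completed treatment or discontinued the study.

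Label: wrong as written, low impact.

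**What to change.** In SAP 2.7.1, replace the merged RECIST sentence with the two protocol rules:

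- CR: two determinations of CR at least 4 weeks apart before progression.
- PR: two determinations of PR or better at least 4 weeks apart before progression, not qualifying for CR.

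Reword the irRC sentence in 2.7.1 to match 4.3.3, or refer to that section. State that DOR and TTR use the same confirmed BOR. Correct the Appendix 14.3 reference for tumour response in 2.7.2 so that it points to the response appendices, 14.1 and 14.2. Check that the dataset specification applies the protocol rule, using PR-CR-PD as a test case.

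The cost is a few sentences in a SAP amendment and one programming check. No new data are needed, and no rule is introduced that the protocol does not already contain.

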2.7.2 Efficacy evaluation

Analysis of efficacy endpoints will be performed separately for the single agent LAG525 arm and for the combo arm using the FAS.

Evaluation of tumor response will be based on investigator assessment according to RECIST v1.1 and irRC [[CLAG525X2101C Amendment 10 Appendix 14.3](#)].

Efficacy endpoints will include ORR, PFS, DOR and DCR as per RECIST V1.1 and per irRC, for phase I and phase II.

For irRC the key difference from RECIST in the assessments of these endpoints is the requirement for confirmation of PD no less than 4 weeks after the criteria for PD are first met. The date of the first of these two assessments is then the date of confirmed progression. For patients who have ended treatment without a valid confirmation assessment, for the purposes of analysis the single assessment of PD will be treated as a confirmed PD. A single assessment of PD followed by a subsequent assessment of SD or better will be considered as a pseudo-progression, and will not be used for analysis. Individual lesion measurements and overall response assessments will be listed by patient and assessment date. Best overall response per RECIST 1.1 and per irRC will be listed and tabulated.

For all efficacy parameters, data will be listed, summarized, or analyzed by treatment group for the phase I part, and by disease group (groups 6 to 10 and 12 to 16) for phase II patients treated at the MTD(s)/ RP2D(s).

BOR and ORR will be summarized by treatment group for all patients treated in the phase I part. The following analyses will be presented by disease group for patients treated in the phase II part.

- BOR will be summarized
- ORR and DCR will be summarized with an accompanying [90%] exact binomial confidence interval (CI)
- For PFS the survival function will be estimated using the Kaplan-Meier (KM) product limit method and displayed graphically. Median duration, with a two-sided [90%] CI, and 25th and 75th percentiles ([Brookmeyer et al 1982](#), [Klein et al 1997](#)) will be presented. KM estimates of survival proportions at specified time points, along with corresponding [90%] CIs (Greenwood's formula, [Kalbfleisch et al 1980](#)) will also be provided.
- For DOR, KM estimates may be provided if at least 10 patients respond in each dosing regimen/indication.

PFS, along with DOR and time to response (TTR) for patients who experience a CR or PR at any time on study, will be listed by patient. Median PFS time and the proportion of patients who are progression-free at 3, 6, 9, and 12 months will be estimated for each group.

For patients who switched from single agent LAG525 to combination with PDR001, the efficacy information will be censored at the date of last adequate assessment before the switch. All efficacy assessments after the switch will be listed and flagged.

2.7.3 Waterfall plot for best overall response and best percentage change from baseline for all target lesions for each patient

The waterfall plot per RECIST 1.1 for all patients is the sum of the longest diameter of all target lesions for each patient by treatment. The FAS will be used to depict anti-tumor activity by treatment.

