#### **6.2.3.2.1 Switch to LAG525 in combination with PDR001 for patients treated with LAG525 single-agent**

Upon disease progression, patients assigned to LAG525 monotherapy during dose escalation may switch to LAG525 + PDR001 at a combination dose level that uses the patient's same LAG525 dose and has been determined safe and tolerable in previous dose escalation patients. If there is no combination dose level that includes the patient's LAG525 monotherapy dose, the patient may receive a lower dose level of LAG525 when switching to LAG525 in combination with PDR001; alternatively, the patient may switch to the LAG525 + PDR001 recommended Phase II dose, once the RP2D has been established. Patients switching to combination therapy must have completed at least 4 cycles of LAG525 monotherapy with no toxicity of CTCAE grade  $\geq 2$  considered related to study treatment.

PDR001 may be added to LAG525 treatment only after documented discussion and agreement between Novartis and the Investigator, based on each patient's condition and review of the planned dose and schedule.

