For patients switching from single-agent LAG525 to combination, efficacy endpoints (like BOR, ORR, PFS, etc.) will be censored at the time the patients start receiving PDR001. All efficacy assessments from these patients will be listed and the assessments performed under combination will be flagged.

Any additional analyses of efficacy endpoints will be described in the RAP.

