4.3.2.2 Confirmed progression

Confirmed progression 1 (type 1, cPD1) is declared if a patient has 2 consecutive tumor assessments at least 4 weeks (28 days) apart both showing disease progression. Assessments with an UNK response or PD assessments < 28 days after initial PD, are discarded.

The first PD is flagged as cPD1 while all subsequent PDs are flagged as xPD1.

The table below shows two hypothetical data scenarios and programming instructions.

Sequence of assessments	Instructions
1 irPD 2 irUNK 3 irPD (Assessment 1 + 30 days)	
 Assessment 3 is ≥ 28 days after Assessment 1 Assessment 3 represents confirmation of irPD at assessment 1 Assessment 1 irPD is flagged cPD1 Assessment 3 irPD is flagged xPD1
1 irSD 2 irPD 3 irPD (Assessment 2 + 20 days) 4 irPD (Assessment 2 + 30 days)	
 Assessment 3 is < 28 days after Assessment 2 Assessment 4 is ≥ 28 days after Assessment 2 Assessment 4 represents confirmation of irPD at assessment 2 Assessment 2 irPD is flagged cPD1 Assessment 3 and 4 irPDs are flagged xPD1

Confirmed progression 2 (type 2, cPD2) is declared if a patient discontinues treatment following a single PD with no subsequent assessments ≥ 28 days later. Assessments with an UNK response or PD assessments < 4 weeks (28 days) after initial PD, are discarded. Discontinuation of treatment is obtained from EOT case report form.

The assessment is flagged as cPD2 and subsequent PDs (<28 days after first PD) are flagged as xPD2.

The table below shows two hypothetical data scenarios and programming instructions.

Sequence of assessments	Instructions
1 irSD 2 irPD - EOT	
 • Patient withdraws after initial progression (Assessment 2) without confirmation • Assessment 2 irPD is flagged as cPD2
1 irPD 2 irPD (Assessment 1 + 20 days) - EOT	
 • Assessment 2 irPD is <28 days after Assessment 1, so does not represent confirmation • However, patient has completed treatment • Assessment 1 irPD is flagged cPD2 • Assessment 2 irPD is flagged xPD2

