4.3.4.2 Definition of start and end dates for time to event variables

Assessment date

Assessment date is defined as for RECIST v1.1 ([\[CLAG525X2101C Amendment 10 Appendix 14.1\]](#)).

Start date

Start date is as defined for RECIST v1.1 ([\[CLAG525X2101C Amendment 10 Appendix 14.1\]](#)).

End dates for time to event variables

The end dates which are used to calculate 'time to event' variables are defined as follows:

- Date of death (during treatment as recorded on the treatment completion page or during follow-up as recorded on the study evaluation completion page or the survival follow-up page).
- Date of death as recorded on death eCRF
- Date of progression as defined in [Section 4.2.4.1](#).
- Date of last adequate tumor assessment is the date the last tumor assessment with overall lesion response of CR, PR or SD which was made before progression or a censoring reason occurred. In this case the last tumor evaluation date at that assessment is used. If no post-baseline assessments are available (before an event or a censoring reason occurred) the date of start of treatment is used.

Note: for sensitivity analyses of time to event endpoints ongoing Patients with an unconfirmed progression may be censored at time of last assessment.

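### SAP 2.7.2, read literally, censors single-agent switchers before the documented progression that led to the switch, which biases Phase I single-agent PFS upward

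*SAP*

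**What the plan says.** **The switch.** Protocol 6.2.3.2.1 states: "Upon disease progression, patients assigned to LAG525 monotherapy during dose escalation may switch to LAG525 + PDR001". SAP 1.1 repeats the trigger. The same protocol section adds a minimum duration: "Patients switching to combination therapy must have completed at least 4 cycles of LAG525 monotherapy". Switchers continue to have tumour assessments and complete an additional End of Treatment disposition form.

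**Censoring of switchers.** In SAP 2.7.2, "the efficacy information will be censored at the date of last adequate assessment before the switch"; later assessments are listed and flagged. Protocol 10.5.2 uses a different point: "efficacy endpoints (like BOR, ORR, PFS, etc.) will be censored at the time the patients start receiving PDR001".

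**The defined term.** SAP 4.3.4.2: "Date of last adequate tumor assessment is the date the last tumor assessment with overall lesion response of CR, PR or SD". Protocol 14.1.25 gives the same definition for RECIST 1.1. A PD scan can never be an adequate assessment.

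**The endpoint.** SAP 2.7.1 and Protocol 14.1.19 both make the first documented progression, or death from any cause, the PFS event. Both reserve censoring at the last adequate assessment for patients who have had no event.

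**The concern.** The reason for switching is normally the PFS event itself. A rule that sends the analysis back to the last CR, PR or SD scan before the switch moves the end date to before that event and records a censoring in its place. Such censoring is informative, because it occurs when and because the patient has progressed.

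The patients affected have had at least 4 cycles of monotherapy, so they supply the later part of the single-agent curve. Protocol Table 3-1 lists PFS among the Phase I secondary endpoints. SAP 2.7.2 calls for Phase I efficacy data to be listed, summarised or analysed by treatment group, and for median PFS and 3-, 6-, 9- and 12-month rates for each group.

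**Working it through.** Neither document states a single-agent PFS figure or the number of switchers, so there is no planned figure to reproduce. The check traces the definitions and then illustrates the size.

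**1. Tracing one switcher.** Take SD at weeks 8 and 16, PD at week 24, then PDR001.
- SAP 2.7.1 and Protocol 14.1.19: event at week 24.
- SAP Table 4-2, situation B, default option: progressed, on the date of progression.
- Protocol 10.5.2: censoring would act only from the first PDR001 dose, after week 24, so the event stands.
- SAP 2.7.1 on alternative cancer therapy: only assessments after the new therapy are dropped, so the event stands.
- SAP 2.7.2, switcher sentence taken literally: censored at week 16.

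Only the last rule reaches back past a documented progression.

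**2. Direction.** Suppose progressions fall on common scan dates. At a scan with n at risk and d progressions, k of them in switchers, the Kaplan-Meier factor is 1 − d/n when they count. It is 1 − (d − k)/(n − k) when they are censored at the previous scan. Since (d − k)/(n − k) < d/n whenever 0 < k ≤ d < n, the curve can only rise.

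**3. Hand example (assumed data).** Ten patients progress at week 8 (five), week 16 (two), week 24 (two) and week 32 (one). One week-24 progressor and the week-32 progressor switch.
- Progressions counted: S(24) = 5/10 × 3/5 × 1/3 = 10%; S(32) = 0.
- SAP sentence: the two switchers are censored at weeks 16 and 24. S(24) = 5/10 × 3/5 × 1/2 = 15%, and the curve stays at 15% at week 32.

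**4. Simulation.**
- From the documents: 134 single-agent patients (Protocol, Amendment 10 study status); scans every 8 weeks to week 40, then every 12 weeks (Protocol 7.2.1); a switch only after 4 × 28 days = 16 weeks.
- Assumed: exponential PFS with a true median of 8, 12 or 16 weeks; a stated fraction of patients with PD at week 16 or later switch; no other censoring; 1,000 runs.

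Six-month PFS, progression counted → SAP sentence:

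| Eligible patients switching | Median 8 wk | Median 12 wk | Median 16 wk |
|---|---|---|---|
| 5% (about 3 to 5 patients) | 12.4 → 13.1% | 24.9 → 25.8% | 35.5 → 36.6% |
| 10% (about 7 to 9) | 12.5 → 13.8% | 25.0 → 27.0% | 35.4 → 37.6% |
| 25% (about 17 to 24) | 12.4 → 16.2% | 25.0 → 30.4% | 35.4 → 41.2% |
| 50% (about 34 to 48) | 12.6 → 22.4% | 25.0 → 37.7% | 35.5 → 48.7% |

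At 10% switching, the 12-month rates move from 1.1 to 1.5%, 5.0 to 6.2% and 10.7 to 12.5%. The 3-month rate does not change, because these switchers progress at week 16 or later. The median stays at the week-8 and week-16 scans for true medians of 8 and 12 weeks. For a true median of 16 weeks, which lies on a scan date, it moves from week 16 to week 24 at 10% switching.

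**5. Early RECIST progression.** A patient with RECIST PD at week 8 who is treated on under irRC and later switches has no earlier post-baseline CR, PR or SD scan, so RECIST PFS would be censored at treatment start. If 5% of week-8 progressors do this (true median 8 weeks, 10% of later progressors switching), the 3-month rate moves from 50.0 to 51.3% and the median from week 8 to week 16. That median shift again arises because the curve sits at about 50% at a scan.

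**6. irRC.** For the type called cPD2, SAP 4.3.2.2 says it "is declared if a patient discontinues treatment following a single PD with no subsequent assessments" at least 28 days later, with discontinuation taken from the End of Treatment form. Switchers complete such a form but continue to be scanned. SAP 4.3.2.1 labels a single irPD followed by irSD or better a pseudo-progression. The SAP does not say whether scans on the combination count for either rule.

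**The case against.** The strongest defence is that PFS is defined event first. SAP 4.3.4.2 places the adequate assessment among those "with overall lesion response of CR, PR or SD which was made before progression or a censoring reason occurred", and the last adequate assessment is the usual censoring date for any patient without an event. On that view SAP 2.7.2 merely supplies the date for the protocol's censoring rule, and a programmer would keep the progression. This reading is possible, but it is not what the sentence says: it is specific to switchers and carries no condition about a prior event.

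Other parts of the defence stand, and they limit the point:
- A reader might infer that every switcher loses an event. The documents do not support that. Protocol 6.2.3.2.1 names no criteria for the progression, and Protocol 7.1.3 recognises progression judged clinically. Under the Table 4-2 default, clinical progression without documentation is ignored, so such a patient has no event to lose and censoring is proper.
- A reader might infer a large distortion. The switch option came with Amendment 08 (21-Jun-2017), whose rationale expects a small number of patients. By 31-May-2017, 133 of the eventual 134 single-agent patients had been treated. The 25% and 50% rows above are therefore bounds, not expectations.
- A reader might extend the point to DOR. SAP 1.1 reports no single-agent antitumour activity, and SAP 2.7.2 makes DOR Kaplan-Meier estimates conditional on at least 10 responders.
- The detailed Kaplan-Meier specification in SAP 2.7.2 is for Phase II, which enrolled only the combination. The exposure is the Phase I listings and any Phase I estimates produced for each group.
- A reader might infer that a response on the combination necessarily erases a single-agent irPD. The additional End of Treatment form and the cPD2 rule partly cover this case; what is missing is a statement that scans on the combination are not used.

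**Conclusion.** The sentence is wrong as written. Applied literally, it converts a progression documented on monotherapy into a censoring, against SAP 2.7.1, Protocol 14.1.19 and the later censoring point in Protocol 10.5.2. Single-agent PFS in Phase I is biased upward, mainly in the 6- to 12-month estimates. The 3-month rate is essentially unaffected and the median often does not move.

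The size cannot be stated, because the number of switchers is not given. If 5% to 10% of eligible patients switched, 6-month PFS would rise by 0.7 to 2.2 points under the assumptions above. At 50% the rise would be 9.8 to 13.2 points, which the timing of Amendment 08 makes implausible. These figures pool all 134 patients; in a small dose group one or two switchers weigh more, as the ten-patient example shows. The DOR effect is negligible. The DLT and Phase II ORR primary analyses are untouched.

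The conclusion assumes that the sentence is programmed as it reads and that the triggering progression was documented. If the programmer applies the event-first definition instead, the result is correct, but the SAP should not leave that choice open.

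**What to change.** Replace the switcher sentence in SAP 2.7.2 with:

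> For patients who switch, assessments after the first PDR001 dose are not used to derive single-agent endpoints, including to confirm or reverse an irPD. A progression documented on or before the first PDR001 dose is an event on its date (a single irPD followed by the switch is treated as cPD2). Only switchers with no documented progression before the first PDR001 dose are censored at the last adequate assessment before the switch.

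The listing and flagging of later assessments can stay as it is. The cost is this wording and one derivation rule, with no new data. Single-agent PFS becomes slightly less favourable. The number of switchers should be reported beside the PFS estimates so that readers can judge how much the rule matters.
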